12. ETHICS

12.1. Ethics Review

The final study protocol, including the final version of the ICF, must be approved or given a favorable opinion in writing by an IRB or IEC, as appropriate. The Investigator must submit written approval to Alnylam Pharmaceuticals, Inc. before he or she can enroll any patient into the study.

The Principal Investigator is responsible for informing the IRB or IEC of any amendment to the protocol in accordance with local requirements. In addition, the IRB or IEC must approve all advertising used to recruit patients for the study. The protocol must be reapproved by the IRB or IEC upon receipt of amendments and annually, as local regulations require.

The Principal Investigator is also responsible for providing the IRB with reports of any reportable serious adverse drug reactions from any other study conducted with the investigational product. Alnylam Pharmaceuticals, Inc. will provide this information to the Principal Investigator.

Progress reports and notifications of serious adverse drug reactions will be provided to the IRB or IEC according to local regulations and guidelines.

12.2. Ethical Conduct of the Study

The study will be performed in accordance with ethical principles that have their origin in the Declaration of Helsinki and are consistent with ICH/GCP, applicable regulatory requirements, and Alnylam Pharmaceuticals, Inc.'s policy.

12.3. Written Informed Consent

The Principal Investigator(s) at each center will ensure that the patient is given full and adequate oral and written information about the nature, purpose, possible risk, and benefit of the study. Patients must also be notified that they are free to withdraw from the study at any time. The patient should be given the opportunity to ask questions and allowed time to consider the information provided.

The patient's signed and dated informed consent must be obtained before conducting any study procedures.

The Principal Investigator(s) must maintain the original, signed ICF. A copy of the signed ICF must be given to the patient.

13. DATA HANDLING AND RECORD KEEPING

13.1. Inspection of Records

Alnylam Pharmaceuticals, Inc. will be allowed to conduct clinical study center visits to the investigation facilities for the purpose of monitoring any aspect of the study. The Investigator agrees to allow the monitor to inspect the drug storage area, study drug stocks, drug accountability records, patient charts and study source documents, and other records relative to study conduct.

13.2. Retention of Records

The Principal Investigator must maintain all documentation relating to the study for a period of at least 2 years after the last marketing application approval, or if not approved 2 years following the discontinuance of the test article for investigation. If it becomes necessary for Alnylam Pharmaceuticals, Inc. or the Regulatory Authority to review any documentation relating to the study, the Investigator must permit access to such records.

14. PUBLICATION POLICY

It is intended that after completion of the study, the data are to be submitted for publication in a scientific journal and/or for reporting at a scientific meeting. A copy of any proposed manuscript must be provided and confirmed received at Alnylam at least 30 days before submission, and according to any additional publication details in the Investigator Agreement.

16. APPENDICES

16.1. Modified Neurological Impairment Score +7 Components

Assessment Tool	Total Points	Components (points)		
Modified NIS+7	304	• Neurologic exam of lower limbs, upper limbs, and cranial nerves (mNIS)		
		 Weakness (192) Reflexes (20) Nerve conduction studies ∑5 (10) 		
		 Ulnar CMAP and SNAP, sural SNAP, tibial CMAP, peroneal CMAP 		
		 Quantitative sensory testing: QST-BSA_{TP+HP} (80) Postural blood pressure (2) 		

Abbreviations: $\sum 5=5$ attributes; CMAP=compound muscle action potential; QST-BSATP+HP=quantitative sensory testing, body surface area, touch pressure plus heat pain; SNAP=sensory nerve action potential.

16.2. Polyneuropathy Disability Score

Stage	Description
0	No symptoms
Ι	Sensory disturbances but preserved walking capability
II	Impaired walking capacity, but ability to walk without a stick or crutches
IIIA	Walking with the help of 1 stick or crutch
IIIB	Walking with the help of 2 sticks or crutches
IV	Confined to a wheelchair or bedridden

16.3. Familial Amyloidotic Polyneuropathy Stage

Stage	Description
0	No symptoms
Ι	Unimpaired ambulation; mostly mild sensory, motor, and autonomic neuropathy in the lower limbs
II	Assistance with ambulation required, mostly moderate impairment progression to the lower limbs, upper limbs, and trunk
III	Wheelchair-bound or bedridden; severe sensory, motor, and autonomic involvement of all limbs

16.4. New York Heart Association Classification of Heart Failure

Class	Symptomology
Ι	No symptoms. Ordinary physical activity such as walking and climbing stairs does not cause fatigue or dyspnea.
II	Symptoms with ordinary physical activity. Walking or climbing stairs rapidly, walking uphill, walking or stair climbing after meals, in cold weather, in wind, or when under emotional stress causes undue fatigue or dyspnea.
Ш	Symptoms with less than ordinary physical activity. Walking 1 to 2 blocks on the level and climbing more than 1 flight of stairs in normal conditions causes undue fatigue or dyspnea.
IV	Symptoms at rest. Inability to carry on any physical activity without fatigue or dyspnea.

	100	Normal no complaints; no evidence of disease
Able to carry on normal activity and to work; no special care needed.	90	Able to carry on normal activity; minor signs or symptoms of disease
	80	Normal activity with effort; some signs or symptoms of disease
Unable to work; able to live at home and care for most personal needs; varying amount of assistance needed.	70	Cares for self; unable to carry on normal activity or to do active work
	60	Requires occasional assistance, but is able to care for most of his personal needs
	50	Requires considerable assistance and frequent medical care
Unable to care for self; requires	40	Disabled; requires special care and assistance
	30	Severely disabled; hospital admission is indicated although death is not imminent
equivalent of institutional or hospital care; disease may be progressing rapidly.	20	Very sick; hospital admission necessary; active supportive treatment necessary
progressing ruptury.	10	Moribund; fatal processes progressing rapidly
	0	Dead

16.5. Karnofsky Performance Status

#### Alnylam Pharmaceuticals, Inc. Statistical Analysis Plan, Protocol ALN-TTRSC-005 11 August 2016, Final Version 2.0

7.4.	Statistical Table Shells	
7.5.	Figure Shells	
7.6.	Data Listing Shells	

Abbreviation	Definition	
AE	Adverse event	
ALT	Alanine transaminase	
AST	Aspartate transaminase	
ATC	Anatomic therapeutic class	
ATTR	Transthyretin-mediated amyloidosis	
COMPASS	Composite Autonomic Symptom Score	
CI	Confidence interval	
CRO	Contract research organization	
CSR	Clinical study report	
DMC	Data Monitoring Committee	
ECG	Electrocardiogram	
eCRF	Electronic Case Report Form	
EOS	End of study	
EQ-5D-5L	European quality of life questionnaire – 5 dimensions – 5 levels	
FAP	Familial amyloidotic polyneuropathy	
HP	Heat pain	
ICH	International Conference on Harmonisation	
ISR	Injection site reaction	
KPS	Karnofsky Performance Status	
LFT	Liver function test	
mBMI	Modified body mass index	
MedDRA ®	Medical Dictionary for Regulatory Activities	
mNIS	Modified neurological impairment score	
NCS	Nerve conduction studies	
NIS	Neurological impairment score	
NYHA	New York Heart Association	
OLT	Orthotopic liver transplant	
РК	Pharmacokinetic(s)	
PND	Polyneuropathy disability	
QOL	Quality of life	
QOL-DN	(Norfolk) Quality of Life Diabetic Neuropathy	
QST	Quantitative sensory testing	
Rel Day	Relative study day	
SAE	Serious adverse event	
SAP	Statistical analysis plan	
SC	Subcutaneous(ly)	
SD	Standard deviation	

# LIST OF ABBREVIATIONS AND DEFINITION OF TERMS

Abbreviation	Definition	
SI	International system of units	
SOC	System organ class	
TEAE	Treatment-emergent adverse event	
TP	Touch pressure	
TTR	Transthyretin	
ULN	Upper limit of normal	
WHO	World Health Organization	

# 1. INFORMATION FROM THE STUDY PROTOCOL

### **1.1.** Introduction and Objectives

#### 1.1.1. Introduction

Refer to Protocol ALN-TTRSC-005 for details on the disease overview, overview of revusiran, and study rationale. A brief overview of the study design is provided below in Section 1.2.

#### 1.1.2. Document and Study Objectives

This statistical analysis plan (SAP) is designed to outline the methods to be used in the analysis of study data in order to address the study objectives. Populations for analysis, data handling rules, statistical methods, and formats for data presentation are provided. The statistical analyses and summary tabulations described in this SAP will provide the basis for the results sections of the clinical study report (CSR) for this trial.

This SAP will also outline any substantial differences in the currently planned analyses relative to those planned in the study protocol (see Section 5). Any substantial changes made to the planned analyses after finalization of the SAP will be described in the CSR.

#### 1.1.2.1. Primary Objective

The primary objective of this study is to assess the efficacy of revusiran in patients with Transthyretin (TTR)-mediated Familial Amyloidotic Polyneuropathy (FAP) with disease progression post-orthotopic liver transplant (OLT) by evaluating the reduction in serum TTR level compared to baseline.

#### 1.1.2.2. Secondary Objectives

The secondary objectives of the study are as follows:

- Evaluate the safety and tolerability of revusiran when administered to TTR-mediated FAP patients with disease progression post-OLT;
- Characterize the pharmacokinetics (PK) of revusiran;
- Describe the effect of revusiran on neurologic impairment.

#### 1.1.2.3. Exploratory Objective

The exploratory objectives of this study are to evaluate the effect of revusiran on various clinical activity parameters including quality of life (QOL), disease stage, modified body mass index (mBMI), and cardiac function.

#### 1.2. Study Design

#### 1.2.1. Synopsis of Study Design

This is a multicenter, multinational, open-label study designed to evaluate the efficacy, safety, and PK of subcutaneously (SC) administered revusiran in patients with TTR-mediated FAP with disease progression post-OLT. It is anticipated that patients from approximately 5 clinical study centers will participate in this study.

Eligible, consenting patients will receive 5 daily doses of revusiran (Days 0 through 4) and a dose at Day 7, followed by once weekly doses for the duration of the study.

Visits will be held at the clinical study center for the following visits, as stated in the schedule of assessments in the protocol: Screening Period (Day -42 to Day -1), Predose Assessments (Day 0), and Daily Dosing (Days 0 through 4) as well as each month for the first 3 months, and approximately every 3 months through Month 18 (or Early Termination), and at the End of Study (EOS) (approximately 28 days after the last dose). The remaining study visits may be conducted at the clinical study center or in the patient's home.

The primary objective of this study will be evaluated by the collection of serum samples for the measurement of total TTR levels. TTR samples will be collected prior to study drug administration, and then assessed on a monthly basis for 3 months, approximately every 3 months thereafter, and at Early Termination.

Adverse events (AEs) will be collected throughout the treatment period and at the EOS visit.

Patients will participate in this study for approximately 21 months (inclusive of a 42-day screening period and a follow-up visit 28 days after the last dose of study drug) and will be treated with study drug for 18 months.

An independent Data Monitoring Committee (DMC) will be implemented for the study and will operate under a prespecified charter.

1.2.2. Randomization Methodology

This is an open-label, single-arm study; therefore, randomization is not applicable.

1.2.3. Stopping Rules and Unblinding

1.2.3.1. Stopping Rules

No stopping rules are prespecified in the protocol to stop the trial early for either harm or benefit.

1.2.3.2. Unblinding

Unblinding does not apply in this open-label study.

#### 1.2.4. Study Procedures

The schedule of assessments is outlined in Table 1 of the study protocol.

1.2.5. Efficacy, Pharmacokinetic, Safety and Exploratory Endpoints

#### 1.2.5.1. Primary Endpoint

The primary endpoint is the percent reduction from baseline in serum TTR level at 6 months.

#### 1.2.5.2. Secondary Endpoints

The secondary endpoints of the study are the change from baseline over 18 months for the following:

- Serum TTR;
- mNIS+7;
- Norfolk Quality of Life-Diabetic Neuropathy (QOL-DN) Questionnaire;
- PND Score.

#### 1.2.5.3. Pharmacokinetic Assessments

Blood samples will be obtained for the assessment of plasma levels of revusiran. Exploratory analyses may also be conducted on plasma samples to evaluate metabolites of revusiran.

Pharmacokinetic parameter estimates using the concentration time data will be performed by Alnylam. All tabulations of PK data will be presented in a PK and PK/PD report separate from the CSR.

#### 1.2.5.4. Safety Assessments

The safety of revusiran will be evaluated by:

- AEs, including liver allograft rejection;
- Vital sign measurements;
- Clinical laboratory evaluations;
- 12-lead electrocardiogram (ECG);
- Physical examinations;
- Ophthalmology examinations;
- Concomitant medications, including immunosuppressive agent monitoring.

#### 1.2.5.5. Exploratory Endpoints

The exploratory endpoints of the study are the assessment of change from baseline over 18 months for the following:

- mBMI;
- FAP stage;
- Grip strength;
- New York Heart Association (NYHA) classification;
- Karnofsky Performance Status (KPS);
- Echocardiogram parameters;
- Cardiac biomarkers;
- EuroQoL questionnaire in 5-dimensions;
- Composite Autonomic Symptom Score (COMPASS) 31 questionnaire;
- Columbia Suicide Severity Rating Scale questionnaire;
- Pharmacoeconomics questionnaire;
- Optional exploratory residual liver tissue evaluation.

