The primary endpoint of the percent reduction from baseline in serum TTR level at 6 months is an objective measurement and not susceptible to bias of clinical study center staff or study patients and therefore does not require a blinded placebo group for accurate interpretation. Secondary endpoints include TTR reduction over 18 months compared to baseline, modified Neurological Impairment Score (mNIS+7), NIS, Norfolk Quality of Life Diabetic Neuropathy (QOL-DN) questionnaire, and polyneuropathy disability (PND) score.

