3.4.5. Exploratory Endpoints

The exploratory endpoints of the study are to assess the change from baseline over 18 months for the following:

- mBMI
- FAP Stage
- NIS
- Grip Strength Test
- NYHA classification
- Karnofsky Performance Status
- Echocardiogram (ECHO) parameters
- Cardiac biomarkers
- EuroQoL questionnaire in 5-dimensions (EQ-5D)
- Composite Autonomic Symptom Score (COMPASS) 31 questionnaire
- Columbia Suicide Severity Rating Scale Questionnaire
- Pharmacoeconomics questionnaire
- Optional exploratory residual liver tissue evaluation

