10.2.3.2. Secondary Efficacy Endpoints

The secondary endpoints of the study are the change from baseline over 18 months for the following: serum TTR, mNIS+7, Norfolk QOL-DN, and PND score.

For continuous parameters, measurements will be summarized using descriptive statistics. Actual measurement, change, and percentage change from baseline to each scheduled visit will be summarized. To understand the effect of revusiran, the mean change from baseline at 18 months with the associated 80% and 95% CIs will also be summarized.

For categorical parameters, frequencies and percentages will be presented. To understand the effect of revusiran from baseline, the frequency and percentage of patients at each of the category shifts from baseline at 18 months will be summarized.

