10.2.3.3. Exploratory Endpoints

The exploratory endpoints of the study are to assess the change from baseline over 18 months for the following: mBMI, FAP stage, NIS, a grip strength test, NYHA classification, Karnofsky Performance Status, ECHO parameters, cardiac biomarkers, EQ-5D and COMPASS 31 questionnaires, and an optional exploratory residual liver tissue evaluation, if available. Analyses for these endpoints will be conducted in a similar fashion as specified for secondary efficacy endpoints.

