#### 4.3.3. Exploratory Endpoints

Analyses of secondary efficacy endpoints will be based on the Evaluable Analysis Set and Safety Analysis Set, except as noted in Section 2.1.

Descriptive statistics will be provided for actual values, change from baseline and percent change from baseline at each scheduled visit for continuous exploratory endpoints. For categorical values, the numbers and percentages of patients reporting each response will be generated.

For QOL questionnaires, summaries of each of the domains will also be generated.

Shift tables will be created for FAP stage to summarize the baseline value versus post-baseline value at each scheduled visit. An additional summary will present the shift from baseline to worst post-baseline value. Similar summaries will be provided for NYHA classification and KPS. For KPS, the categories will be defined as follows: 100-80 (able to carry out normal activity and to work; no special care needed), 70-50 (unable to work; able to live at home and care for most personal needs; varying amount of assistance needed) and 40-0 (unable to care for self; requires equivalent of institutional or hospital care; disease may be progressing rapidly).

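### The SAP leaves the NIS total score, a protocol exploratory endpoint, out of its endpoint list and planned summaries and does not declare the change

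*SAP*

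**What the plan says.** Protocol 3.4.5 opens its list with "The exploratory endpoints of the study are to assess the change from baseline over 18 months for the following" and gives NIS its own bullet. The statistics section, Protocol 10.2.3.3, names it again ("mBMI, FAP stage, NIS, a grip strength test, NYHA classification") and adds: "Analyses for these endpoints will be conducted in a similar fashion as specified for secondary efficacy endpoints". For continuous secondary endpoints, Protocol 10.2.3.2 asks for by-visit summaries and says that "the mean change from baseline at 18 months with the associated 80% and 95% CIs will also be summarized".

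Protocol 1.3 places NIS one tier higher. Its sentence on secondary endpoints includes "modified Neurological Impairment Score (mNIS+7), NIS, Norfolk Quality of Life Diabetic Neuropathy (QOL-DN) questionnaire, and polyneuropathy disability (PND) score".

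SAP 1.2.5.5 restates the exploratory endpoints ("The exploratory endpoints of the study are the assessment of change from baseline over 18 months for the following") without NIS. The SAP's four secondary endpoints (1.2.5.2) do not include it either. SAP 4.3.3 covers its list generically: "Descriptive statistics will be provided for actual values, change from baseline and percent change from baseline at each scheduled visit for continuous exploratory endpoints". On departures from the protocol, SAP 1.1.2 says: "This SAP will also outline any substantial differences in the currently planned analyses relative to those planned in the study protocol (see Section 5". Section 5 itself names no departure and refers to the study report.

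**The concern.** A protocol endpoint has dropped out of the analysis plan without a word. Patients still undergo the examination: Table 1 of the protocol schedules NIS at Screening, Screening/Baseline, Baseline, Months 6, 12 and 18 and Early Termination, and Protocol 8.3.3 asks for two independent assessments at each time point. If the programmers follow the SAP text, the report will summarise neither the NIS total nor its sensation part.

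That matters for interpretation. The study has one arm, so any reading of neurological change leans on outside rates. Protocol 1.1.2.2 gives one neurological-score rate for patients who progress after transplant, 8.84 points per year, and it is on the NIS scale. Without an NIS summary the report has no score on that scale to set beside it. NIS is also the score on which patients are selected (5 to 130, Protocol 4.1).

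**Working it through.** No sample-size or power figure is involved. The check compares the lists item by item, then asks whether any other SAP text restores what is missing.

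**Step 1. Compare the lists.** Protocol 3.4.5 has 13 items: mBMI, FAP stage, NIS, grip strength, NYHA class, Karnofsky status, echocardiogram, cardiac biomarkers, EQ-5D, COMPASS 31, the Columbia scale, pharmacoeconomics and residual liver tissue. SAP 1.2.5.5 has the same items in the same order without NIS: 13 − 1 = 12. The SAP adds none.

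**Step 2. Look for NIS elsewhere in the SAP.**

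| SAP section | What it plans |
|---|---|
| 1.2.5.2 | Serum TTR, mNIS+7, Norfolk QOL-DN, PND; no NIS |
| 4.2 | Baseline mNIS+7; no NIS total |
| 4.3.2 | NIS-Weakness, NIS-Reflexes, nerve conduction, QST and postural blood pressure, as mNIS+7 components |
| 4.3.3 | Generic text that depends on the 12-item list |
| 5 | No specific change named |
| 6 | Scoring entries 6.1 to 6.8; none for NIS |
| 3.10 | All recorded data listed, so patient-level NIS would appear |
| 7 | Headings only in the public text |

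**Step 3. Can the total be rebuilt from the planned component tables?** Protocol 8.3.3 defines NIS as including sensation as well as weakness and reflexes. Protocol 8.2.1 notes that sensation does not count in the mNIS+7 score. Appendix 16.1 confirms this by its points: weakness 192 + reflexes 20 + nerve conduction 10 + QST 80 + postural blood pressure 2 = 304, which equals the stated total. No points are left for NIS sensation, so the component tables cannot yield a summary of the NIS total.

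**Step 4. Would restoring the bullet be enough?** It would bring NIS under SAP 4.3.3, which gives by-visit statistics. SAP 4.3.3 plans no Month 18 confidence intervals for any continuous exploratory endpoint, whereas Protocol 10.2.3.3 points back to 10.2.3.2, which includes 80% and 95% intervals. That gap covers the whole exploratory tier.

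**Step 5. Would the NIS baseline be defined?** Not clearly. SAP 3.2 averages replicates and gives grip and mNIS+7 as examples. SAP 3.4 takes the last value before first dose for clinical outcomes and reserves averaging of all predose values for TTR and vitamin A. NIS has paired assessments before dosing, so the two rules need to be read together, and the SAP does not say how.

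**The case against.** The best defence is that little is lost. NIS is a descriptive exploratory endpoint in a study of about 12 patients. Its weakness and reflex parts are the same as in mNIS+7 and are summarised. For sensation, Protocol 8.3.3 itself regards QST as more quantitative and broader than the NIS sensory sub-score, and QST is summarised. All of this stands, and it limits the loss to the NIS total and its sensation part.

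A second defence is that this is a copying slip. SAP Section 1 presents itself as information taken from the protocol, and the protocol's own lists vary: 10.2.3.3 names 11 items and omits the Columbia scale and the pharmacoeconomics questionnaire. The table shells might contain NIS. That is possible, but a table in the shells would not correct the SAP text, which neither lists the endpoint nor declares its removal.

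A third is that the protocol's reference to a similar fashion of analysis is too loose to promise confidence intervals. That is a fair reading, but because 10.2.3.3 refers back to the secondary analyses, the SAP should settle the question for the whole tier.

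A reader might infer that NIS was removed deliberately, since the study is open-label and the SAP (11 August 2016) is later than Protocol Amendment 2 (9 March 2016). The documents do not support that. They give no reason at all, and an oversight fits them equally well. A reader might also infer that the secondary objective on neurologic impairment goes unanswered. It does not: mNIS+7 is the secondary neurological endpoint and is fully summarised, and no text ties NIS by name to that objective.

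**Conclusion.** The SAP text is wrong as written on this point. It omits 1 of 13 protocol exploratory endpoints, plans no summary of the NIS total or NIS sensation, and declares no change although it says that substantial differences are outlined in Section 5. Whether this difference is substantial is a judgement; that it is undeclared is a fact.

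The correction is minor to moderate. No primary or safety result changes, most of the underlying examination is summarised under mNIS+7, and patient-level values would be listed. The practical loss is a summary on the scale of the 8.84-per-year figure. The protocol plans no formal comparison with that figure. It also quotes a grip-strength decline of 22% per year, and grip strength remains in the SAP.

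The conclusion rests on the public SAP text. If the unpublished shells include an NIS table, what remains is a mismatch between text and shells, to be corrected in the text. The missing Month 18 intervals should not be read as particular to NIS; they are missing for every continuous exploratory endpoint.

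**What to change.** 1. Add NIS total score to SAP 1.2.5.5, so that SAP 4.3.3 provides its by-visit values, changes and percentage changes, and show NIS sensation separately. If removal was intended, declare and justify it in Section 5 instead.
2. In SAP 4.3.3, add the Month 18 mean change with 80% and 95% confidence intervals for all continuous exploratory endpoints, including NIS, not for NIS alone.
3. State how the replicate-averaging rule (SAP 3.2) and the closest-predose baseline rule (SAP 3.4) work together for the paired NIS assessments before first dose.
4. Reconcile the tier of NIS between Protocol 1.3 (secondary) and Protocol 3.4.5 and 10.2.3.3 (exploratory).

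The cost is a few lines of text, one summary table for NIS, and interval columns in tables already planned. The data are already scheduled, so no visit or assessment is added.
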